6. EXAMINATION OF SUBGROUPS

No prespecified evaluation of subgroups will be performed.

7. STUDY POPULATION

7.1. Subject Disposition

Subject disposition will be tabulated for all screened subjects and will include:

- the number of subjects dosed in the original parent study (NEOD001-201; NEOD001 Safety Population)
- the number of subjects screened in the OLE
- the number screened but not enrolled in the OLE
- the number enrolled in the OLE (OLE Safety Population)
- the number in each organ evaluable population
- the number who discontinued treatment early in the OLE and reason(s) for discontinuation of treatment as recorded on the OLE eCRF
- the number who withdraw from OLE study prior to completing the study and reason(s) for withdrawal as recorded on the OLE eCRF

By-subject data listings of all the above study disposition data including study completion and any reasons for premature treatment and/or study withdrawal will be presented.

7.2. Demographics and Baseline Characteristics

Demographic and baseline characteristics from as reported on the OLE Demographics eCRF will be summarized for the OLE Safety Population.

Demographic variables will include the following:

- Age at informed consent including the subgroups <65 vs ≥ 65 years
- Sex
- Race
- Ethnicity

Other baseline characteristics will include the following:

- Weight (kg)
- Height (cm)
- BMI (kg/m^2) including frequency of the following subgroups: <20, ≥ 20 - <25, ≥ 25 - <30, ≥ 30 kg/m^2
- Both conventional BMI and modified BMI (mBMI [$\text{kg}/\text{m}^2 \times \text{g}/\text{L}$], defined as subject's weight (kg)/subjects squared height (meters) \times serum albumin (g/L)) will be presented.

No inferential statistical comparisons will be performed.

All demographic and baseline characteristics data will be presented in by-subject data listings.

7.3. Baseline AL Amyloidosis Disease Characteristics

The following disease histories from the original parent study (NEOD001-201) will be summarized for the OLE Safety Population:

- Age at AL amyloidosis diagnosis
- Duration (months) since AL amyloidosis diagnosis
- Number of prior regimens for amyloidosis
- Duration (months) since last reported therapy for amyloidosis
- Response to last reported therapy for amyloidosis (CR, VGPR, PR, NR)
- Best response to previously reported therapy (CR, VGPR, PR, NR)
- Duration (months) since best response to previously reported therapy for amyloidosis
- Number of derived involved organs (1 or 2 organs: renal, peripheral neuropathy) as defined in [Section 5](#)
- Number of physician assessed involved organs: The Investigator also assessed other organ involvement including gastrointestinal, autonomic nervous system, lung, soft tissue/lymphatic, or other. (1, 2, 3, 4, or 5 organs)
- Total number of involved organs (derived plus physician assessed)
- Screening and Baseline NT-proBNP (ng/L)
- Baseline 6MWT distance (meters)
- Renal Stage ([Appendix 11](#)): I, II, III; I/II, III; I, II/III
- Chronic Kidney Stage: 1, 2, 3, 4, 5
- NYHA Class ([Appendix 4](#)): I, II, III, IV; I/II vs III/IV
- Baseline FLC Ratio: Low (<0.26), Normal (0.26 – 1.65), High (>1.65)

No inferential statistical comparisons will be performed.

Baseline disease characteristics will be presented in by-subject data listings.

7.4. General Medical History

Medical history verbatim terms as recorded on the OLE eCRFs will be mapped to preferred terms (PTs) and system organ classes (SOCs) using MedDRA version 19.0.

General medical history will be presented in a by-subject data listing.

7.5. Prior and New Concomitant Medications

Medication verbatim terms as recorded on the OLE eCRFs will be mapped to Anatomical Therapeutic Chemical (ATC) class and Preferred Name using the WHO Drug Dictionary, B2 Enhanced December 2015.

Prior concomitant medications are those medications started prior and continued after the first infusion of study drug in the OLE. New concomitant medications are those medications that were started on or after the first infusion of study drug in OLE. If it cannot be determined whether the medication was a new concomitant medication due to a partial start or stop date or if the medication is taken on the same date as the first infusion of study drug, then it will be counted as a new concomitant medication.

Prior and new concomitant medications will be presented in a by-subject data listing.

7.6. Protocol Deviations

The Investigator is not permitted to deviate from the protocol in any significant way without prior notification to the Sponsor (or designee) as described in the protocol.

All protocol deviations will be collected by the clinical research associates and presented in a by-subject data listing.

7.7. Chemotherapy

Chemotherapy regimens may be prescribed as per standard of care at the Investigator's discretion. All chemotherapy recorded on the Prescribed Chemotherapy Regimens and Concomitant Chemotherapy Treatment Medications eCRFs will be listed for OLE Safety Population.

7.8. Concurrent Procedures

Data will be collected for concurrent procedures will be mapped to PTs and SOCs using MedDRA version 19.0. and will include name of procedure, ongoing status, indication, relationship to an AE or medical history, and frequency of the procedure. Concurrent procedures will be displayed in a subject data listing only for OLE Safety Population.

8. EFFICACY ANALYSES

All recorded efficacy endpoint data will be presented in by-subject data listings for the OLE Safety Population.

Analyses will be produced in both NEOD001 Safety Population and OLE Safety Population, unless otherwise specified. Data, visit window, and treatment group to be used for each population as below:

1. NEOD001 Safety Population:
 - Data: Pooled data from parent and OLE study
 - Visit window: PRONTO visit window for data in parent study, OLE therapy visit window for OLE data with exclusion of OLE Baseline.
 - Treatment: Placebo and NEOD001 subjects received in NEOD001-201 study and Overall
2. OLE Safety Population:
 - Using data from OLE study only
 - Visit window: OLE therapy visit window
 - Treatment: NEOD001

Analyses in Renal Evaluable Population or Peripheral Neuropathy Evaluable Population will be presented in the same manner described above for NEOD001 Safety Population and OLE Safety Population.

Baseline in all efficacy analyses refers to PRONTO Baseline and OLE Baseline, unless otherwise specified.

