8.4 Analysis of Efficacy Endpoints

Response rates will be summarized including 95% confidence intervals. The distributions of time-to-event endpoints (progression-free survival, overall survival) will be summarized using the Kaplan-Meier method.

All quantitative endpoints (except 6MWT distance) defined as the change from baseline will be analyzed using linear mixed models for repeated measurements (MMRM). The dependent variable will be the change from baseline at each time point. The model will include fixed effects for time point and treatment-by-time interaction. The baseline value of the corresponding endpoint will be included as a covariate and the unstructured covariance model will be used. The denominator degrees of freedom will be estimated using the Kenward-Roger approximation. The 6MWT distance change from baseline will be analyzed using a Wilcoxon signed rank test.

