5. ANALYSIS POPULATIONS

The NEOD001 Safety Population will include all subjects who received any amount of NEOD001 in the original parent study (NEOD001-201).

The OLE Safety Population will include all subjects who received any amount of NEOD001 in the OLE study.

The Renal Evaluable Population will include subjects who were in the Renal Evaluable Population in the original parent study (NEOD001-201), defined as subjects who had proteinuria >0.5g/24 hours (measured by 24-hour urine total protein excretion), at baseline and at least one post-baseline assessment of proteinuria in NEOD001-201.

The Peripheral Neuropathy Evaluable Population will include subjects who were in the in the Peripheral Neuropathy Evaluable Population in the original parent study (NEOD001-201), defined as subjects who had ascending sensorimotor neuropathy due to AL amyloidosis etiologies at screening, had a baseline Neuropathy Impairment Score–Lower Limbs (NIS-LL) total score of 2 or greater and at least one post-baseline NIS-LL total score in NEOD001-201.

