8.6.3. NT-proBNP Endpoint: Change from Baseline

Change from baseline will be analyzed using a REML based MMRM model including a fixed effect for categorical time point and with the baseline value included as a covariate. The unstructured covariance model will be used. If the computational algorithm fails to converge, the following structures will be executed: heterogeneous Toeplitz, Toeplitz, heterogeneous First-Order Autoregressive [AR(1)], AR(1), heterogeneous compound symmetry (HCS), and compound symmetry (CS). The covariance structure converging to the best fit, as determined by Akaike’s information criterion (AIC), will be used. The Kenward and Roger method will be used to calculate the denominator degrees of freedom for the test of fixed effects. All visits will be

included in the model. Estimates of least-square (LS) means, standard errors (StdErr), and 95% CIs will be presented at each visit.

Descriptive statistics for NT-proBNP, change from baseline, and percent change from baseline will be presented by visit.

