9.3. Adverse Events

Verbatim terms on the OLE Adverse Event eCRFs will be mapped to PT and SOC using MedDRA version 19.0. AEs will be reported, and severity will be categorized using the Common Terminology Criteria for Adverse Events (CTCAE, Version 4.03).

All AE summaries will be restricted to treatment-emergent adverse events (TEAEs), which are defined as any AE that newly appears, increases in frequency, or worsens in severity following initiation of study drug and up to 30 days after date of last dose or last study visit, whichever is

later. If it cannot be determined whether the AE is treatment emergent due to a partial onset date, then it will be counted as such.

To assess the long-term treatment effects overall and relative to shorter term treatment, TEAE incidence will be summarized separately by the original parent study (NEOD001-201) and OLE study (NEOD001-OLE251) as shown in Table 6. TEAEs collected during original parent study will be summarized by actual treatment subjects received. TEAEs that start on or after the first dose of OLE study will be summarized by treatment group subjects received in parent study. Overall summary will also be presented for NEOD001-OLE251.

Table 6: Treatment Group Schema

NEOD001-201		NEOD001-OLE251		
NEOD001 (N=xx)	Placebo (N=xx)	NEOD001-201 NEOD001 (N=xx)	NEOD001-201 Placebo (N=xx)	Overall (N=xx)

Each AE summary will be presented according to Table 6 for All Treated Subjects. Summaries that are displayed by SOC and PT will be ordered by descending order of NEOD001-OLE251 overall incidence of SOC and PT within each SOC.

- An overall summary of AE incidences will be presented, including the number and percent of subjects with at least one of:
 - Any TEAE
 - TEAE by maximum CTCAE Grade
 - CTCAE Grade ≥ 3 TEAE
 - Serious TEAE
 - Fatal TEAEs (outcome="Fatal" or severity=CTCAE Grade 5)
 - Treatment-related TEAE
 - Treatment-related serious TEAE
 - Treatment-related TEAE of CTCAE \geq Grade 3
 - TEAE leading to infusion interruption
 - TEAE leading to dose reduction
 - TEAE leading to dose being held
 - TEAE leading to prolongation of infusion time (>2.5 hours)
 - Infusion associated TEAE as determined by the Investigator
 - TEAE leading to study drug withdrawal
- Subject incidence of TEAEs by MedDRA SOC and PT
- Subject incidence of serious TEAEs by MedDRA SOC and PT

The following listings will be presented by subject for OLE Safety Population:

- All AEs

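### The OLE-only efficacy analyses pool former-placebo and continuing subjects in one NEOD001 column, and neither the companion by-arm analysis nor the MMRM clearly restores the split

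*SAP*

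**What the plan says.** SAP Section 8 sets up two parallel sets of efficacy analyses.

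- **Item 1, NEOD001 Safety Population.** "Data: Pooled data from parent and OLE study", with columns given as "Treatment: Placebo and NEOD001 subjects received in NEOD001-201 study and Overall". Parent data use the PRONTO visit windows. OLE data use the OLE windows, with OLE Baseline left out as a visit.
- **Item 2, OLE Safety Population.** "Using data from OLE study only", with one column: "Treatment: NEOD001". SAP 5 defines the population: "The OLE Safety Population will include all subjects who received any amount of NEOD001 in the OLE study".

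The renal and peripheral neuropathy subsets follow the same two layouts. Section 8 closes by naming both PRONTO Baseline and OLE Baseline as references for the efficacy analyses.

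On the model, Protocol 8.4 says: "The model will include fixed effects for time point and treatment-by-time interaction", with baseline as a covariate. SAP 8.6.3 specifies an MMRM "including a fixed effect for categorical time point and with the baseline value included as a covariate". The same model serves SF-36v2 PCS (8.7), creatinine, proteinuria and eGFR (8.9.3) and NIS-LL (8.10). SAP 10, on changes to the protocol's analyses, lists removed analyses and does not mention the model.

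For safety, SAP 9.3 takes a different line from item 2: "TEAEs that start on or after the first dose of OLE study will be summarized by treatment group subjects received in parent study". Table 6 adds an Overall column.

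**The concern.** NEOD001-201 was placebo-controlled, so OLE entrants arrive with two exposure histories. Except for the 6MWT, which keeps its PRONTO Baseline, OLE Baseline is the last assessment before the first OLE infusion (SAP 2.2.4.2). For former-placebo subjects it precedes NEOD001. For continuing subjects it follows the parent-study course of drug. The same NT-proBNP response rule therefore measures initial response in one cohort and further change after prior treatment in the other. A single LS mean or response rate mixes the two, and its value depends on how many of each cohort enrolled. A reader could take a weak pooled change as little effect in new starters, or as continued improvement in treated subjects, and the table could not show which.

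**Working it through.** The documents state no sample size calculation, alpha or effect size (SAP 3; Protocol 8.6), so there is no planned figure to reproduce. The check sets the sections side by side and then illustrates the size.

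**1. Exposure gap.** The parent study has monthly visits through Month 12 (SAP 4.6.1, Table 2: Month 12 target Day 308, final visit target Day 338). With the SAP's own conversion, 308 / 30.4375 = 10.1 months and 338 / 30.4375 = 11.1 months. With no missed doses, and counting the infusion given at the visit, cumulative NEOD001 infusions are:

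| OLE month | Former placebo | Continuing |
|---|---|---|
| 6 | 6 | 6 + 12 = 18 |
| 12 | 12 | 12 + 12 = 24 |
| 24 | 24 | 24 + 12 = 36 |
| 36 | 36 | 36 + 12 = 48 |

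The gap is up to 12 infusions at every visit. In relative terms it is largest early: 18/6 = 3 times at Month 6, against 48/36 = 1.33 times at Month 36.

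**2. Does anything else restore the split?**

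- *Subgroups:* SAP 6 plans none.
- *Item 1 population:* SAP 5 defines it as subjects who received NEOD001 in the parent study. Read literally, item 1's Placebo column is empty, and former-placebo subjects appear only in item 2. SAP 7.1 equates the same population with the subjects dosed in the parent study, which points the other way.
- *Item 1 reference:* its windows omit OLE Baseline as a visit, while Section 8 names both baselines as references. Change from OLE Baseline by arm is neither clearly planned nor clearly excluded.
- *Item 1 model:* SAP 8.6.3 has visit and baseline only, and does not say whether arms are fitted separately or jointly. A joint fit gives one LS mean per visit, not one per arm. Separate fits would give arm-specific means.

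**3. Model against protocol.** The protocol has time point, treatment-by-time and baseline. The SAP has time point and baseline. SAP 10 is silent on the difference.

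**4. Size (illustration on assumed inputs).** Let w be the former-placebo share. The documents do not give the parent allocation, so w is taken from 1/3 to 2/3.

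Pooled mean = w x (former-placebo mean) + (1 - w) x (continuing mean).

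If former-placebo subjects change by -d and continuing subjects have plateaued at 0, the pooled mean is -wd: -d/3 at w = 1/3, -d/2 at w = 1/2, -2d/3 at w = 2/3.

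If the cohorts differ by 0.5 SD, the pooled mean is off by (1 - w) x 0.5 for former-placebo and w x 0.5 for continuing subjects: 0.33 and 0.17 SD at w = 1/3, 0.25 and 0.25 at w = 1/2, 0.17 and 0.33 at w = 2/3.

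**5. What a split would show.** Take about 100 subjects (Protocol 3.3), SD 1, one visit and no dropout. The 95% half-width for the difference between cohorts is 1.96 x sqrt(1/n1 + 1/n2). At 50/50 it is 1.96 x sqrt(0.02 + 0.02) = 0.39 SD. At one-third to two-thirds it is 1.96 x sqrt(0.03 + 0.015) = 0.42 SD. That is enough to describe the cohorts, though small differences would stay unresolved.

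**The case against.** The strongest reply is that item 1 already plans the by-arm display. It carries OLE visits, splits them by parent arm, adds Overall, and extends to the organ subsets. A reader of item 2 alone might infer that all OLE efficacy is shown as one group, and the text does not support that. Nor does leaving OLE Baseline out of item 1's windows show that it is dropped as a reference value: that wording governs visits in the series.

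A reader might also infer that the plan throws away a randomised early-versus-delayed-start comparison. That goes too far. Such a contrast is read from PRONTO Baseline, which belongs to item 1. Entrants must have completed the parent study and met OLE eligibility, so the arms at OLE entry are selected cohorts. The protocol sets no controlled comparison here: its synopsis and Section 3.4 mark control group and randomisation as not applicable.

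On the model, the protocol never says what treatment means in a single-drug study. With one level, as in item 2, a treatment-by-time term cannot be estimated, so its absence there follows from the pooling. Parent arm is the evident two-level candidate, but the protocol does not name it.

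Finally, a shortened report after the programme was discontinued may reasonably include an all-treated column.

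These points narrow the concern to item 2 and to the gaps in item 1. They do not remove it. Item 1's population definition contradicts its own Placebo column, its model may not yield arm-specific means, and an all-treated column can stand beside the split.

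**Conclusion.** The point holds in limited form. Item 2 pools two cohorts whose exposure differs by up to 12 infusions, so its change and response from OLE Baseline describe neither. Item 1 would largely cover the gap if its population includes parent-placebo subjects, if change from OLE Baseline is shown by arm, and if the model allows for arm. The SAP does not settle any of the three. The dropped treatment-by-time term is mainly a documentation gap for item 2 and a real ambiguity for item 1.

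The -d/3 to -2d/3 range rests on an assumed plateau and an assumed share, and the SD figures rest on assumed cohort differences. They show how pooling acts and are not estimates for this trial. Any comparison of the cohorts is descriptive. No hypothesis test or error rate is at stake; what suffers is the interpretability of the long-term efficacy tables.

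**What to change.** 1. In SAP 8 item 2, present OLE Safety Population efficacy in the Table 6 layout: parent NEOD001, parent placebo, Overall. State that change and response from OLE Baseline are shown this way.
2. In SAP 8.6.3, add parent arm and parent-arm-by-visit to the MMRM, or state that arms are fitted separately. Sections 8.7, 8.9.3 and 8.10 then inherit the change.
3. Reconcile the NEOD001 Safety Population definition in SAP 5 with item 1's Placebo column, by widening the definition or by renaming the population.
4. Record in SAP 10 how the model differs from Protocol 8.4.
5. State that contrasts between parent arms in the OLE are descriptive, because entrants are eligible parent-study completers.

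The cost is SAP wording and table shells. Parent treatment is already needed for Table 6, so no new data or variables are required, and the Overall column is kept.

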8.1. Adjustments for Covariates

For analyses of change from baseline, restricted maximum likelihood (REML) based mixed-effect model for repeated measures (MMRM) or analysis of covariance (ANCOVA) models will be used and the corresponding baseline value will be used as a covariate in the model.

8.2. Handling of Dropouts or Missing Data

For the SF-36v2, missing data conventions for partially completed questionnaires are specified in [Section 2.3.2.2](#).

The following methods will be implemented to address missing data for relevant efficacy endpoint analyses.

8.2.1. Time to All-Cause Mortality

Subjects with no data after randomization will be censored on Day 1 (first day of study drug dosing).

8.2.2. Responder Endpoints

For analyses of best response, a subject missing response status will be considered as a non-responder for 2-category response (response, non-response), or progressed for a 3-category response (response, stable, progression).

For analysis for response at each visit, analyses will use “observed cases,” where subjects who do not provide an assessment at the specified time point for the defining of response will not be included. That is, for the percentage of responders, the subject will not be included in the numerator or the denominator.

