 - Notes: NT-proBNP should be drawn before conducting 6MWT if being performed on the same calendar day. If the 6MWT is conducted on the same calendar day as the study drug infusion, the 6MWT must be completed before initiation of the infusion
- 12-lead ECG in triplicate (perform centrally) – within 30 minutes before start of dosing – every 3 months
- Laboratory Assessments (central laboratory, unless otherwise noted):
 - Hematology and chemistry (including amylase and creatine kinase) per [Appendix 10](#)
 - Coagulation - PT/INR, PTT
 - Other coagulation indices – Month 1, Month 12 - per [Appendix 11](#)
 - **Month 1:** EOS/ETD results from Study NEOD001-201 will serve as baseline for this study. Collect sample for vWF activity and antigen assays before dosing on Month 1-Day 1 if they were not tested at EOS/ETD in Study NEOD001-201.
 - **Month 12:** *For subjects with defects identified at EOS/ETD in Study NEOD001-201:* collect sample and test analytes that were abnormal. *All other subjects:* collect sample. If defects are identified, additional analytes will be evaluated, as indicated.
 - Troponin T
 - NT-proBNP
 - Note: NT-proBNP should be drawn before conducting 6MWT if being performed on the same calendar day
 - Urine pregnancy test (WOCBP only)
 - sFLCs – every 6 months
 - Serum IFE and PEP – every 6 months
 - Urinalysis - dipstick per [Appendix 10](#) – every 6 months
 - 24-hour urine collection - every 6 months for:
 - Urine IFE and PEP
 - Urine protein excretion

- Other Assessments (see Laboratory Manual):
 - NEOD001 serum sample – within 2 hours before infusion – every 6 months (± 1 month)
 - Anti-NEOD001 serum sample – preinfusion – every 3 months

Study Drug Administration:

Subjects who present with symptomatic orthostatic hypotension and/or systolic BP < 85 mmHg, which in the medical judgment of the Investigator would interfere with the subject's ability to safely receive treatment, will have study drug withheld until the next scheduled monthly administration, but should still have all other study visit assessments completed. If study drug is withheld and subsequently rescheduled, central laboratory assessments required for that visit will need to be repeated if they were drawn > 7 days prior to the rescheduled dosing date. A symptom-directed physical exam and vital signs need to be repeated prior to each dosing.

- Month 1-Day 1:

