2.3.2.1. NT-proBNP (Cardiac) Endpoints

The following endpoints will be evaluated in the NEOD001 Safety Population and OLE Safety Population (see Section 5).

For these subjects, cardiac response, as assessed by N-terminal pro-brain natriuretic peptide (NT-proBNP), categories are defined as (modified from Table 2 in [Comenzo, 2012; Appendix 2](#)):

Response	Stable Disease	Progression
Decrease in NT-proBNP from baseline of >30% and >300 ng/L	Assessment was neither Response nor Progression	Increase in NT-proBNP from baseline of >30% and from baseline >300 ng/L

Best response is defined as the most favorable category (response, stable, or progression) across all visits. Subjects will be classified as responders or non-responders. Non-response is defined as either stable or progression.

- Cardiac best response from PRONTO and OLE baselines (see Section 2.2.4), as assessed by NT-proBNP response criteria. Best response will be over the course of the study.
- Cardiac response from PRONTO and OLE baselines (see Section 2.2.4), as assessed by NT-proBNP response criteria, at each visit
- Change and percent change from PRONTO and OLE baselines (see Section 2.2.4) to each visit in NT-proBNP

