2.3.2.4. Renal Endpoints

The following endpoints will be evaluated in the Renal Evaluable Population (see Section 5).

For these subjects, renal response categories (modified from [Palladini, 2014](#) ; [Appendix 2](#)) are defined as:

Response	Stable	Progression
≥ 30% decrease from baseline or < 0.5g/24 hours post-baseline result of proteinuria (measured by 24-hour urine total protein excretion) in the absence of renal progression	Assessment was neither Response nor Progression	≥ 25% decrease in eGFR from baseline Note: if assessment qualifies as both Response and Progression, then assessments will be counted as progression

Best response is defined as the most favorable category (response, stable, or progression) across all visits. Subjects will be classified as responders or non-responders. Non-response is defined as either stable or progression.

- Renal best response from PRONTO and OLE baselines (see Section 2.2.4). Best response will be evaluated over the course of the study
- Renal response from PRONTO and OLE baselines (see Section 2.2.4) at each visit
- Change and percent change from PRONTO and OLE baselines (see Section 2.2.4) to each visit in creatinine, proteinuria, and estimated glomerular filtration rate (eGFR)

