4. GENERAL STATISTICAL METHODS

4.1. Reporting Conventions

Individual subject data obtained from electronic case report forms (eCRFs), central laboratories, external sources, and any derived data will be presented in data listings by subject. The primary data source will be used for all analyses. All data listings that contain an evaluation date will contain a relative study day. Pre-treatment and on-treatment study days are numbered relative to the day of the first dose of study drug in the OLE which is designated as Day 1. The preceding day is Day -1, the day before that is Day -2, etc.

All output will be incorporated into Microsoft Word rich text format (.rtf) files, sorted and labeled according to the International Council for Harmonisation (ICH) recommendations, and formatted to the appropriate page size(s).

For categorical variables, summary tabulations of the number and percentage of subjects within each category (with a category for missing data) of the parameter will be presented. Percentage calculations will be based on non-missing data, unless otherwise specified. Percentages are rounded to 1 decimal place, unless otherwise specified.

For frequency counts of categorical variables, categories whose counts are zero will be displayed for the sake of completeness. For example, if none of the subjects discontinued due to “lost to follow-up,” this reason will be included in the table with a count of 0. Percentages based on frequency counts will be presented to one decimal place, and values less than 1% will be presented as “<1%.” Values less than 100% but greater than 99% will be presented as “>99%.”

For continuous variables, the number of subjects, mean, standard deviation (SD), median, 25th quartile (Q1), 75th quartile (Q3), minimum, and maximum values will be presented. The precision of summary statistics, unless otherwise specified will be as follows: mean and median to 1 more decimal place than the raw data, and SD to 2 decimal places more than the raw data. In general, the number of decimal places should not exceed 3 decimal places unless appropriate. Confidence intervals (CIs) will be provided and will be rounded to 1 decimal place, unless otherwise specified, in the table and listing shell.

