8.6. NT-proBNP (Cardiac) Endpoint Analyses

8.6.1. Best Response from Baseline

Best response will be derived from Baseline. All visits after the first infusion of study drug will be included. The number and percentage, with associated two-sided exact (Clopper-Pearson) 95% CIs, of subjects in each category of best response (response, nonresponse) will be presented. Refer to [Section 8](#) for details about course of the study and relative first infusion of study drug for each set of analyses.

Cardiac response as 3 categories (response, stable, and progression) will be presented in the same manner described above.

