8.9.1. Best Renal Response from Baseline

Best renal response will be analyzed in the same manner described [Section 8.6.1](#).

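### Subjects with no best-response status are counted as progressed in the three-category table, mixing unobserved outcomes into the progression row

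*SAP*

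**What the plan says.** SAP 8.2.2 has two rules for a missing best-response status. In the two-category display the subject is a non-responder. In the three-category display the subject is counted as follows: "or progressed for a 3-category response (response, stable, progression".

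The three-category display is kept for the heart (SAP 8.6.1): "Cardiac response as 3 categories (response, stable, and progression) will be presented in the same manner described above". That manner is a count, a percentage and a Clopper-Pearson 95% CI. For the kidney, SAP 8.9.1 says "Best renal response will be analyzed in the same manner described" in 8.6.1. SAP Section 10 lists the analyses dropped after the program was discontinued, and neither display is among them.

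SAP 2.3.2.1 defines the endpoint: "Best response is defined as the most favorable category (response, stable, or progression) across all visits". SAP 2.3.2.4 uses the same definition for the kidney.

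Two general statements point the other way. SAP 4.1 promises, for categorical variables, "summary tabulations of the number and percentage of subjects within each category (with a category for missing data". Protocol 8.7 puts observed data in the summary tables and mentions imputation only as a possible sensitivity analysis. Section 10 does not list the 8.2.2 rule as a change.

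**The concern.** The progression row would be read as the share of subjects whose disease progressed and never showed anything better. Under 8.2.2 it also holds subjects about whom nothing is known, and the table carries no count that separates the two groups. The CI then describes the sum of an outcome and a data gap.

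The kidney shows the problem most plainly because its two criteria come from different tests on different schedules. Progression is "≥ 25% decrease in eGFR from baseline", and eGFR comes with monthly chemistry. Response needs 24-hour protein, and Protocol 6.1.2 lists "24-hour urine collection - every 6 months for" that test. A subject can therefore have several eGFR values that rule out progression and still have no urine result from which to judge response.

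**Working it through.** **Inputs**

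- Missing status becomes progressed: SAP 8.2.2.
- Best response is the best category at any visit: SAP 2.3.2.1 and 2.3.2.4.
- Renal progression uses eGFR only; renal response needs 24-hour protein; stable is whatever meets neither definition: SAP 2.3.2.4.
- Chemistry, including eGFR, is monthly; 24-hour urine is six-monthly and at EOS/ETD: Protocol 6.1.2, 6.1.3 and Appendix 10.
- Renal Evaluable entry requires "at least one post-baseline assessment of proteinuria in NEOD001-201", that is, in the parent study and not in the extension: SAP 5.
- The OLE Safety analysis uses extension data only; the NEOD001 Safety analysis pools parent and extension data: SAP 8.
- CI method: Clopper-Pearson, SAP 8.6.1.
- Planned enrolment: about 100, Protocol 3.3.
- Missing rates and number of renal-evaluable subjects: not in the documents, so assumed below.

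The plan states no figure for this row, so there is none to reproduce.

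**Step 1. Who is in the row.** Let N be the subjects in the table, P those who progressed at every classifiable visit, and M those with no classifiable visit.

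Tabulated progression = (P + M) / N.

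One stable or responding visit takes a subject out of P. Nothing takes a subject out of M.

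**Step 2. A renal subject traced through the rules (extension data only).** OLE Baseline eGFR is 60. The progression threshold is 0.75 × 60 = 45. eGFR lies between 57 and 62 at Months 2 to 5, so the largest fall is (60 − 57)/60 = 5%. The subject then leaves without an ETD urine collection.

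- If a visit with eGFR but no urine has missing status, no visit is classifiable, and 8.2.2 tabulates progression.
- If such a visit counts as stable, best response is stable.

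The SAP does not choose between these readings. On the first, the only progression criterion was measured and not met, yet the table reports progression.

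**Step 3. Size with no true progression in the row.** For x = P + M, the lower limit is the 2.5th percentile of Beta(x, N − x + 1), or 0 if x = 0. The upper limit is the 97.5th percentile of Beta(x + 1, N − x). With N = 50 assumed and P = 0:

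| M | Tabulated progression | 95% CI |
|---|---|---|
| 0 | 0/50 = 0% | 0 to 7.1 |
| 5 | 5/50 = 10.0% | 3.3 to 21.8 |
| 10 | 10/50 = 20.0% | 10.0 to 33.7 |

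**Step 4. Size with some true progression.** Take N = 100 with 10 assumed missing, and 10% of the 90 assessed subjects in the row, so P = 9.

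- SAP rule: (9 + 10)/100 = 19.0% (11.8 to 28.1).
- Separate missing row, all subjects as denominator: 9/100 = 9.0%.
- Observed cases: 9/90 = 10.0% (4.7 to 18.1).

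The number of responders, and N, are the same under the SAP rule and the separate row.

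**The case against.** The rule is explicit, prespecified and a worst case, so it cannot flatter the drug, and a specific section may override a general reporting convention. No hypothesis test depends on the row, the program has ended, and progression-free survival and time to progression were dropped. All of that stands and limits the importance of the point. It does not justify reporting an unobserved outcome as progression, since the two-category display already carries the conservative handling.

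A reader might also infer more than the documents support:

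- **That both analysis sets are affected alike.** In the pooled analysis from PRONTO Baseline, the entry rule in SAP 5 already guarantees a post-baseline proteinuria result. The kidney case belongs mainly to the extension-only analysis.
- **That by-visit renal response is distorted too.** SAP 8.2.2 uses observed cases there and leaves out subjects without the assessment that defines response. That most naturally excludes visits with eGFR only.
- **That cases cannot be traced.** Subject listings and by-visit summaries would let a careful reader find them. The table alone does not show them.
- **That missing subjects must make up most of the row.** This depends on assumed rates. In a simulation (12 monthly visits, log-eGFR SD 0.06, a true 40% fall in 20% of subjects, eGFR-only visits without a fall treated as missing), 10% leaving before Month 6 and 20% of those lacking ETD urine gave a row of 11.4%. Only 17% of it never had a 25% fall. With 50% and 50%, the row was 31.1% and the share 77%. The result largely returns its inputs.

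Urine and NT-proBNP are required at EOS/ETD (Protocol 6.1.3), and Protocol 4.4 seeks those tests from withdrawals when possible. NT-proBNP is monthly, so a missing cardiac status requires no usable post-baseline value at all. Actual numbers may be small.

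**Conclusion.** The point holds as a reporting defect. Following 8.2.2 as written adds subjects with no status to the progression row, inflates it by M/N, and does not show M. This departs from the missing category in SAP 4.1 and from Protocol 8.7.

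The cardiac case follows directly from the text. The renal case rests on two readings: that 8.9.1 carries the three-category display over, and that a visit with eGFR only has missing status. It is confined mainly to the extension-only analysis.

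The number affected cannot be derived from the documents. The shift from 0% to 10.0% is an illustration with 5 missing among an assumed 50. The response rate and subject safety are not touched. The change should be made, but nothing else in the plan depends on it.

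**What to change.** 1. In SAP 8.2.2, keep missing as non-responder for the two-category display. For the three-category display, replace the progressed rule with a separate not-evaluable row. State that all subjects in the population are the denominator; SAP 4.1 bases percentages on non-missing data unless told otherwise, so it does not supply this.
2. In SAP 2.3.2.4, class a renal visit as progression whenever eGFR has fallen at least 25% from baseline, with or without urine. Require 24-hour protein to class a visit as response or stable. Subjects with no classifiable visit are not evaluable. Requiring both tests at every visit would be wrong, because it would discard measured eGFR progression.
3. Footnote the progression row as progression at every evaluable visit.

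The cost is one table row, one footnote and a few sentences, with no new data. A reader who wants the worst case must add two rows. The renal rule is also asymmetric: a subject with stable eGFR-only months, one measured 25% fall and no urine stays in the progression row. The footnote makes that visible.
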